# 3.3.5 Definition of Peanut Oral Allergy Syndrome

Peanut Oral Allergy Syndrome (OAS) will be diagnosed using the following criteria:

An indeterminate or positive Visit 144 OFC with symptoms limited to typical OAS symptoms will be independently reviewed by allergists not participating in the OFC. A diagnosis of OAS without primary peanut allergy will made based on the following criteria:

- OAS symptoms after eating an additional non-peanut food typically associated with OAS
- Birch sensitisation on SPT (≥3 mm) or SpIgE (≥0.35 kU/L)
- Ara h components consistent with diagnosis of OAS in the absence of primary peanut allergy as per the definition in section 3.3.1
- No prior history of primary peanut allergy

A negative Visit 144 OFC with symptoms limited to typical OAS symptoms will be considered OAS if the participant additionally meets the following criteria:

- OAS symptoms after eating an additional non-peanut food typically associated with OAS
- Birch sensitisation on SPT (≥3 mm) or SpIgE (≥0.35 kU/L)

• Ara h components consistent with diagnosis of OAS in the absence of primary peanut allergy as per the definition in section 3.3.1

A participant that does not undergo an OFC, but is deemed not allergic as per the definition in section 3.3.1 will be considered to have OAS if the following criteria are met:

- OAS symptoms after eating peanut and an additional non-peanut food typically associated with OAS
- Birch sensitisation on SPT ( $\geq$ 3 mm) or SpIgE ( $\geq$ 0.35 kU/L)
- Ara h components consistent with diagnosis of OAS in the absence of primary peanut allergy as per the definition in section 3.3.1

# 3.4 DATA AND SAFETY MONITORING AND STOPPING RULES

## 3.4.1 Ongoing Review

The protocol chair, the DAIT/NIAID medical monitor, the ITN clinical trial physician, and the NIAID Allergy and Asthma Data and Safety Monitoring Board (DSMB) will review safety data on an ongoing basis and at least annually. The DSMB may stop enrollment or participation in the trial at any time if it concludes that there are significant safety concerns.

## 3.4.2 Stopping Rules Guidance

## 3.4.2.1 Study-related Adverse Events

Enrollment in the trial will be stopped pending review (1) if any death occurs or (2) if two participants are admitted to an intensive care unit for an adverse event related to study participation.

Oral food challenges will be stopped pending review if two oral food challenges result in anaphylaxis associated with hypotension or hypoxia as defined in section 8.2.2 and which does not respond to two epinephrine injections.

# 3.5 STUDY DURATION

This study will commence in 2018 with data collection continuing until August 31, 2022. This will allow for the enrolment of former LEAP participants aged 12 years.

The LEAP siblings and parents cohorts will be enrolled concurrently with the LEAP participant cohort.

Study duration will be 234 weeks:

- Enrollment phase will be 234 weeks (4 years, 6 months).
- Study participation phase will be 1 visit.

## 4. ELIGIBILITY

## 4.1 LEAP PARTICIPANTS

## 4.1.1 Inclusion Criteria – LEAP Participants

Individuals must meet *all* of the following criteria to be eligible for this cohort in the study:

- 1. Participation in LEAP.
- 2. Age at least 114 months (9.5 years).
- 3. Willingness to participate in at least one study data collection (i.e. questionnaire, skin pricking testing, or blood draw) procedure.
- 4. Assent by child and informed consent by parent or legal guardian. For participants only returning a Questionnaire in any format, assent/informed consent will be implied. For participants only completing a telephone visit, assent/informed consent will be given verbally.

## 4.1.2 Exclusion Criteria – LEAP Participants

There are no exclusion criteria for LEAP Participants.

## 4.2 LEAP SIBLINGS

## 4.2.1 Inclusion Criteria – LEAP Siblings

Individuals must meet *all* of the following criteria to be eligible for this cohort in the study:

- 1. Sibling of LEAP participant.
- 2. Willingness to participate in at least one study data collection (i.e. questionnaire, skin pricking testing, or blood draw).
- 3. Assent by child and informed consent by parent or legal guardian if child is younger than 16; siblings aged 16 and over will provide their own consent. For participants only returning a Questionnaire in any format, assent/informed consent will be implied. For participants only completing a telephone visit, assent/informed consent will be given verbally.

#### 4.2.2 Exclusion Criteria – LEAP Siblings

There are no exclusion criteria for LEAP siblings.

## 4.3 LEAP PARENTS

#### 4.3.1 Inclusion Criteria – LEAP Parents

Individuals must meet *all* of the following criteria to be eligible for this cohort in the study:

- 1. Biological parent of LEAP participant.
- 2. Willingness to participate in at least one study data collection (i.e. questionnaire, skin pricking testing, or blood draw).

3. Informed consent. For participants only returning a Questionnaire in any format, informed consent will be implied. For participants only completing a telephone visit, informed consent will be given verbally.

#### 4.3.2 Exclusion Criteria – LEAP Parents

There are no exclusion criteria for LEAP parents.

## 4.4 PREMATURE TERMINATION OF A PARTICIPANT FROM THE STUDY

**Withdrawal of consent.** Participants who withdraw consent for further procedures. These participants will be asked if they would be willing to complete an end-of-study visit to include specific assessments.

**Investigator decision.** The principal investigator may choose to withdraw a participant from the study for any reason.

**Failure to return.** Participants who do not return for visits and who do not respond to repeated attempts by the site staff to have them return will be considered *lost to follow-up*.

## 5. STUDY THERAPIES AND MEDICATIONS

This section does not apply.

## 6. STUDY ASSESSMENTS AND WINDOWS

#### 6.1 VISIT WINDOWS

#### 6.1.1 Scheduled Visits

The schedule of events is in Appendix 1. There is one visit, termed Visit 144.

#### **LEAP Participants**

Visit 144 must take place after the LEAP participant reaches 114 months (9.5 years) of age and before August 31, 2022.

#### Siblings and Parents

Visit 144 must take place before August 31, 2022.

#### 6.1.2 Window to Complete Visit 144

More than one clinic appointment may be required to complete all assessments. The visit must be completed within 8 weeks of enrollment. The visit window does not apply to the telephone visit (Section 6.2.3).

Participants may be asked to return to obtain additional samples in the event the samples were lost, damaged, or not sufficient.

#### 6.1.3 Definition of Enrollment and Study Participation

Enrollment is the time at which a participant is determined to be eligible for participation and signs consent. Study participation is the period from signing consent to the completion of Visit 144 for any single participant. Different members of a family may conclude their participation at different times.

## 6.2 VISIT TYPES

## 6.2.1 Clinic

Clinic visits will take place at the Clinical Trials Research Unit. Assessments listed in sections 6.3 to 6.7 will be conducted.

#### 6.2.2 Home

Home visits will be undertaken when participants who are residents in the UK are unable to attend the Clinical Trials Research Unit. For these home visits the Guy's and St. Thomas' NHS Foundation Trust's "Protection and Support of Lone Workers Procedure" will be in use. The informed consent process and assessments will be the same as those completed at a clinic appointment, as outlined in sections 6.3 to 6.7, except those listed below.

- Peanut oral food challenges will only be performed at home for participants at low risk of a reaction. Any participant who qualifies as being at risk of a peanut reaction (as defined in section 6.7.1) will not have an oral food challenge at home.
- The following assessments will not be conducted at home visits as equipment in the clinic is required to conduct the assessments:
  - TEWL
  - Spirometry
  - Anthropometry (skin fold thickness and waist circumference)

## 6.2.3 Telephone

Telephone visits will be undertaken when participants are not able to or do not wish to come into the clinic or have a home visit. The assessments will be the same as those completed at a clinic appointment, except as noted below. Informed consent will be given verbally during the telephone visit.

Additionally, verbal consent will be requested for the clinic staff to obtain peanut SPT and IgE allergy assessment results performed in the last year by contacting the clinic where the tests were performed. IgE results will be accepted for those undertaken in standardized labs using Thermo Fisher Scientific ImmunoCap System. The following assessments will not be conducted due to the visit not being conducted in person.

- Physical Exam
- SCORAD
- Urine pregnancy test
- TEWL
- Spirometry
- Allergy Assessments specified in Section 6.5, except those performed in the last year and obtained as specified above or obtained through home collection kits detailed below.

Participants who undergo a telephone visit may subsequently undergo an in person clinic visit or home visit. The assessments not included in the telephone visit will be conducted at the in person visit. In addition, parts of the telephone assessments may be repeated at the clinic visit or home visit at the discretion of the site investigator.

For participants who are unable to attend the study site or undergo a home visit, blood may be collected at home to complete Allergy Assessments detailed in 6.5. Collection will be done via finger prick or home collection kit, using either a lancet finger prick device and/or micro-needle capillary blood collection device. The methodology for collection of the specimen and postal return to the Laboratory will be explained by telephone. Samples may be subsequently stored for analyses as detailed in section 7.

## 6.3 GENERAL ASSESSMENTS

## 6.3.1 Non-dietary Assessments

The following general assessments will be performed:

- Informed consent: Informed consent will be obtained before any study procedures are performed. For children younger than 16, assent will also be obtained.
- Eligibility criteria.
- Medical history.
- Physical examination: Temperature, pulse, respiratory rate, weight and height will be completed for LEAP participants and siblings <18 years of age. Skin fold thickness and waist circumference measurements will only be taken for LEAP participants.
- Urine pregnancy test on all post-menarcheal participants prior to undergoing an incremental oral food challenge.
- Concomitant medications: All concomitant medications will be recorded on the CRFs.
- Eczema: SCORAD: Both subjective and objective eczema severity criteria will be recorded. The modified SCORAD evaluation alone will be used for all remaining eczema evaluations.
- TEWL: this is a measure of water loss from skin and will be recorded for LEAP participants and siblings.
- Bed dust collection: All families will be sent a vacuum pack with an information sheet, consent forms and instructions on how to collect a dust sample from bed-sheets.
- Rhinoconjunctivitis and Oral Allergy Syndrome (OAS) evaluation: Symptoms in accordance with the study definitions for seasonal and perennial rhinoconjunctivitis and OAS will be recorded.
- Asthma: Symptoms in accordance with the study definition for asthma will be recorded and spirometry measurements taken for LEAP participants and siblings.
- Food reaction history: A history will be taken to determine if the participant has had any clinically significant food-induced, immediate-onset allergic reactions.

- Food Allergy History Questionnaire: A questionnaire relating to the consumption of common food allergens (including tree nuts and sesame), foods that commonly cause OAS symptoms, and any other foods causing reactions indicative of immediate onset food allergy or OAS will be completed for all participants.
- Adverse events: Participants will be assessed for adverse events. Adverse events will be recorded as described in section 8.

## 6.3.2 Dietary Assessments

- Dietary history: A dietary history will be obtained for LEAP participants only using a 3-day food diary that captures typical food consumption around the time of the visit and provides a breakdown of macro- and micronutrient intake and total energy intake.
- Peanut consumption monitoring: Peanut consumption questionnaires will be used to assess all participant's peanut consumption.
- Dietary education: Dietitians will provide dietary advice specific to each participant's allergic profile.

# 6.4 CLINICAL LABORATORY ASSESSMENTS

Routine clinical laboratory assessments are not planned in this study.

# 6.5 ALLERGY ASSESSMENTS

- SPT for peanut (see section 6.6)
- IgE total
- IgE and IgE component resolved diagnosis (CRD) for peanut
- IgG for peanut
- IgG4 and IgG4 component resolved diagnosis (CRD) for peanut
- Peanut oral food challenges
- SPT to ingested allergens by extract to include hen's egg white, tree nuts, sesame; fresh food to include hens egg white, and if milk and sesame equivocal on extract, fresh milk and tahini
- SPT to inhaled allergens by extract to include Timothy grass, birch pollen, alternaria mould, cat and dog dander, and dust mite (*Dermatophagoides pteronyssinus*)
- Sp-IgE to ingested allergens to include hen's egg white, cow's milk, peanut, sesame, Brazil nut, walnut, cashew and almond
- Sp-IgE to inhaled allergens to include dust mite, cat, dog, alternaria, Timothy grass and birch pollen

# 6.6 SKIN-PRICK TESTING

Because of the importance of skin prick testing in this study, some details regarding performing this testing are included here.

Prior to testing, ensure that the participant has not received short-acting antihistamine medications for at least 48 hours and/or long-acting antihistamine medications for at least 7 days.

The SPT for raw hen's egg white will be performed using Red Lion salmonella-free egg. The other SPTs will be performed using Soluprick® extracts (ALK-Abelló, where available). Lyophilized peanut extract (ALK-Abelló) will be analyzed for total protein and major peanut allergen concentration (Ara h1, Ara h2, and Ara h3). The extract will be stored at -72 °C and will be used for SPT evaluations to peanut throughout the study. Saline 0.9% will be used as a negative control, and histamine (concentration of 1 mg/mL of saline) will be used as the positive control.

Tests will be performed on the forearm unless unaffected eczema-free skin patches are not available, in which case the skin on the participant's back will be used for testing. Using a standardized lancet (ALK-Abelló), the skin will be pricked through a drop of the extract, which will then be absorbed.

Skin test sites should be measured after 15 minutes. The wheal and erythema should be measured at their widest diameters and recorded separately. Tests will be interpreted based on the widest wheal diameter.

The positive and negative control tests should be performed and measured prior to allergen SPT. If the saline negative control test is  $\ge 3$  mm, then it should be repeated immediately. If the repeat test remains  $\ge 3$  mm, the testing should be rescheduled for approximately 7 days' time. If the histamine positive control is  $\le 3$  mm, then it should be repeated immediately. If the repeat test remains  $\le 3$  mm, then the testing should be rescheduled for expected immediately. If the repeat test remains  $\le 3$  mm, then the testing should be rescheduled for repeated immediately. If the repeat test remains  $\le 3$  mm, then the testing should be rescheduled for approximately 7 days' time.

For peanut measurements, the following rules apply:

- The SPT will be performed in duplicate and the mean of the two tests will be recorded.
- If both results are  $\geq 1$  mm and at least one result is  $\leq 4$ mm, and there is a > 2 mm difference between the results, a third SPT will be performed and the mean of the two closest results will be recorded.
- If one result is < 1 mm and one result is ≥ 1 mm, a third SPT will be performed. If two of three results are < 1 mm, 0 mm will be recorded as the final result. If two of three results are ≥ 1 mm, the mean of those two results will be recorded as the final result.
- When both SPTs are >4mm, the average of the two peanut SPTs will be recorded without necessitating a third SPT even if the difference between the two SPTs is >2mm. If the first or second SPT is <4mm the existing protocol rules for a third SPT apply.

# 6.7 PEANUT CHALLENGES

## 6.7.1 Conduct

Peanut challenges will be conducted for LEAP participants and siblings <18 years of age as either open (unblinded) challenges or double-blind, placebo-controlled food challenges (DBPCFC). If a participant has a positive pregnancy test, the incremental oral food challenge will not be conducted.

Participants who are  $\leq 36$  months of age at the time of the challenge will consume 3.85 g peanut protein during the challenge. Participants who are > 36 months of age at the time of the challenge will consume 9.35 g peanut protein during the challenge.

The open food challenges will be either cumulative (single dose) or incremental (sequentially increasing doses), depending on the participant's risk of a peanut-induced allergic reaction. Participants are considered as being at risk of a peanut reaction if they meet one or more of the following criteria:

- they have had a previous peanut-induced allergic reaction,
- they have no known previous ingestion of peanut and also have a SPT (as per above methodology) of greater than 2 mm to peanut on the day of the challenge, or
- the investigator suspects peanut allergy.

If the participant is considered at risk of a peanut reaction (as defined above), the challenge will be performed as an incremental open challenge (see section 6.7.1.1.1). The participant will consume 3.85 g of peanut protein if they are  $\leq$  36 months of age or 9.35 g of peanut protein if they are > 36 months of age for the incremental open (unblinded) challenge.

If the participant is considered at low risk of a peanut reaction, the challenge will be performed as a cumulative open (unblinded) challenge (see section 6.7.1.1.2). The participant will consume 3.85 g of peanut protein if they are  $\leq$  36 months of age or 9.35 g of peanut protein if they are > 36 months of age for the cumulative open (unblinded) challenge. The participant must consume 3.85 g of peanut protein if they are  $\leq$  36 months of age or a minimum of 5 g of peanut protein if they are > 36 months of age with no allergic symptoms to complete the cumulative open (unblinded) challenge.

A DBPCFC will be performed when the open challenge results in an inconclusive outcome or at the discretion of the investigator (i.e. participant with food aversion or high anxiety). Participants > 36 months of age will consume a total of 9.35 g of peanut protein for the DBPCFC (4.35 g as blinded doses and 5 g as the final open dose). Participants  $\leq$  36 months of age will consume a total of 3.85 g of peanut protein for the DBPCFC (1.85 g as blinded doses and 2.0 g as the final open dose).

A DBPCFC will preferentially be conducted on two separate days (see section 6.7.1.2.1). However, if the family can only attend for a single day, the DBPCFC will be undertaken as a single day mixed challenge with active and placebo doses randomly interspersed (see section 6.7.1.2.2).

The peanut challenge will be discontinued if a reaction occurs that meets the study outcome criteria for a positive challenge (see Table 1 in section 6.7.2) and action will be taken according to local hospital guidelines. After discussion with an investigator, doses may be repeated if subjective or equivocal symptoms occur.

#### 6.7.1.1 Open challenges

#### 6.7.1.1.1 Incremental open challenge

For participants and eligible siblings (i.e. <18 years of age) considered at risk of a peanut reaction, as defined in section 6.7.1 above:

#### For participants $\leq$ 36 months of age (3.85 g):

- Administer 3.85 g of peanut protein in five doses of 0.1, 0.25, 0.5, 1.0, and 2.0 g in separate meals.
- For at risk participants, two lower doses of 0.01 g and 0.03 g peanut protein may be given prior to the usual 0.1 g starting dose at the discretion of the physician.
- After each dose, observe the child for at least 15 minutes. If there is no reaction, administer additional peanut doses.

## For participants > 36 months of age (9.35 g):

- Administer 9.35 g of peanut protein in six doses of 0.1, 0.25, 0.5, 1.0, 2.5, and 5.0 g in separate meals.
- For at risk participants, two lower doses of 0.01 g and 0.03 g peanut protein may be given prior to the usual 0.1 g starting dose at the discretion of the physician.
- After each dose, observe the child for at least 15 minutes. If there is no reaction, administer additional peanut doses.

## 6.7.1.1.2 Cumulative open challenge

# For participants and eligible siblings (i.e. <18 years of age) unlikely to have a peanut reaction :

## For participants $\leq$ 36 months of age (3.85 g):

- Administer 3.85 g of peanut protein within a 6-hour period. The participant must consume complete dose with no allergic symptoms to complete the cumulative open (unblinded) challenge.
- Observe the child during the challenge and for at least 1 hour after completion of the cumulative dose.

## For participants > 36 months of age (9.35 g):

- Administer 9.35 g of peanut protein within a 6-hour period. The participant must consume a minimum of 5 g of peanut protein with no allergic symptoms to complete the cumulative open (unblinded) challenge.
- Observe the child during the challenge and for at least 1 hour after completion of the cumulative dose.

No particular feeding regimen is required. Peanut meals may vary and be used interchangeably.

## 6.7.1.2 Double-blind, placebo-controlled food challenge

DBPCFCs will be conducted for participants where their open (unblinded) challenge outcome is inconclusive, or at the investigator's discretion. The total dose for participants  $\leq$  36 months of age: 3.85g (1.85 g as blinded doses and 2.0g as the final open dose). The

total dose for participants > 36 months of age: 9.35 g (4.35 g as blinded doses and 5 g as the final open dose).

Dose assessments and adjustments:

• The active and placebo meals will be blinded by a computer-generated random code known to the dietician but not to the participant, nurse, or doctor.

#### 6.7.1.2.1 Two-day separate double-blind, placebo-controlled food challenge

Perform the two-day DBPCFC as follows:

#### For participants $\leq$ 36 months of age (3.85 g):

Day 1:

- Administer four blinded doses in increasing increments of 0.1, 0.25. 0.5, and 1.0 g, all of which are either peanut protein or placebo depending on the randomisation. Two lower doses of 0.01 g and 0.03 g peanut protein may be given prior to the 0.1 g dose at the discretion of the physician.
- After each dose, observe the child for at least 15 minutes.

#### Day 2:

- Administer four blinded doses in increasing increments of 0.1, 0.25. 0.5, and 1.0 g, all of which are either peanut protein or placebo depending on the randomisation. If peanut protein was administered on day 1, then administer placebo on day 2, or vice versa. A lower dose of 0.03 g peanut protein may be given prior to the 0.1 g dose at the discretion of the physician.
- After each dose, observe the child for at least 15 minutes.
- If the top blinded dose on day 2 is reached with no allergic reaction, wait 20 minutes and administer an additional open (unblinded) 2.0 g dose of peanut protein.

#### For participants > 36 months of age (9.35 g):

Day 1:

- Administer five blinded doses in increasing increments of 0.1, 0.25. 0.5, 1.0, and 2.5 g, all of which are either peanut protein or placebo depending on the randomisation. Two lower doses of 0.01 g and 0.03 g peanut protein may be given prior to the 0.1 g dose at the discretion of the physician.
- After each dose, observe the child for at least 15 minutes.

Day 2:

Administer five blinded doses in increasing increments of 0.1, 0.25. 0.5, 1.0, and 2.5 g, all of which are either peanut protein or placebo depending on the randomisation. If peanut protein was administered on day 1, then administer placebo on day 2, or vice versa. A lower dose of 0.03 g peanut protein may be given prior to the 0.1 g dose at the discretion of the physician.

- After each dose, observe the child for at least 15 minutes.
- If the top blinded dose on day 2 is reached with no allergic reaction, wait 20 minutes and administer an additional open (unblinded) 5 g dose of peanut protein.

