8.3.9. Secondary Endpoint 7: Peanut allergy

Peanut allergy status in the LEAP Siblings and LEAP Parents at V144 will be determined using the same criteria for the determination of peanut allergy status in LEAP Participants, as described in section 8.2.1.1.

The proportion of LEAP Siblings in the ITT population with peanut allergy will be compared between the LEAP Consumers and LEAP Avoiders using a logistic regression model with a random family effect included to account for the clustering of siblings within family units and the analysis of multiple siblings. Older Siblings and Younger Siblings will be analyzed separately.

The same statistical methodology will be repeated for the LEAP Parents in the ITT population.

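### In the two-day DBPCFC the optional low steps differ by day, so a child whose active day is day 2 is not offered the 0.01 g first step; the text should also say that these steps follow the day's code

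*Protocol*

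**What the plan says.** Protocol 6.7.1.2.1 sets out the two-day DBPCFC separately for children over 36 months and for those of 36 months or younger. The wording on this point is the same in both.

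- **Main doses.** On each day the main blinded doses are "all of which are either peanut protein or placebo depending on the randomisation".
- **Order of days.** Either day can be active: "If peanut protein was administered on day 1, then administer placebo on day 2, or vice versa".
- **Day 1 optional steps.** "Two lower doses of 0.01 g and 0.03 g peanut protein may be given prior to the 0.1 g dose", if the physician chooses.
- **Day 2 optional step.** "A lower dose of 0.03 g peanut protein may be given prior to the 0.1 g dose", again if the physician chooses. The 0.01 g step is absent.

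Protocol 6.7.1.2 gives the general blinding rule: active and placebo meals are "blinded by a computer-generated random code known to the dietician but not to the participant, nurse, or doctor". It does not mention the optional low steps.

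The other two graded formats offer both low steps. In the incremental open challenge (6.7.1.1.1), for at-risk children, "two lower doses of 0.01 g and 0.03 g peanut protein may be given prior to the usual 0.1 g starting dose". The one-day mixed DBPCFC (6.7.1.2.2) offers the same pair.

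On when the procedure is used, Protocol 6.7.1 says: "A DBPCFC will be performed when the open challenge results in an inconclusive outcome or at the discretion of the investigator". The same section makes the two-day form the preferred one.

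**The concern.** There are two faults in the same sentences.

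The first is the difference between the days. The low steps are a precaution for a child who may react to a very small amount. They have a purpose only on the day when peanut is given, and that day is chosen at random. Offering the smallest step on day 1 only means that its availability depends on the order drawn, not on the child's risk. Neither document gives a reason.

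The second is the wording. The clause that makes a dose peanut or placebo is attached to the main doses. The optional doses are in separate sentences that name peanut protein and do not mention placebo or the code. That wording works in the open and one-day formats, which have no placebo day, but it does not fit a format that has one.

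At stake are a small margin of caution for a child with active day 2, and a clean contrast between the blinded parts of the two days.

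**Working it through.** **1. The plan's own totals.** The main doses listed in 6.7.1.2.1 reproduce the totals stated in 6.7.1.2.

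- Over 36 months: 0.1 + 0.25 + 0.5 + 1.0 + 2.5 = 4.35 g blinded; + 5 g open = 9.35 g.
- 36 months or younger: 0.1 + 0.25 + 0.5 + 1.0 = 1.85 g blinded; + 2.0 g open = 3.85 g.

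Both agree, so the stated totals leave out the optional steps.

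**2. The low steps follow the day's code (the likely intent).** The placebo day then has no peanut in its blinded part.

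| | Active day 1 | Active day 2 |
|---|---|---|
| Lowest step offered | 0.01 g | 0.03 g |
| Blinded peanut, over 36 months | 4.35 + 0.04 = 4.39 g | 4.35 + 0.03 = 4.38 g |
| Blinded peanut, 36 months or younger | 1.85 + 0.04 = 1.89 g | 1.85 + 0.03 = 1.88 g |

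Ratio of lowest steps: 0.03 / 0.01 = 3. Difference: 0.03 - 0.01 = 0.02 g. Both are below the usual 0.1 g start (10% and 30% of it).

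**3. The low steps are always peanut (the literal text).** If the steps are used, the blinded part of a placebo day contains:

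- placebo on day 1: 0.01 + 0.03 = 0.04 g;
- placebo on day 2: 0.03 g.

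As a share of the blinded peanut total:

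- over 36 months: 0.04 / 4.35 = 0.9% and 0.03 / 4.35 = 0.7%;
- 36 months or younger: 0.04 / 1.85 = 2.2% and 0.03 / 1.85 = 1.6%.

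**4. The low steps are given only on the active day.** This does not work either. The extra meals would mark that day, and the physician who decides on the steps does not hold the code.

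**5. Does tolerating day 1 make 0.01 g unnecessary on day 2?** If day 1 was placebo, tolerating it says nothing about peanut. If day 1 was active, day 2 is placebo and needs no precautionary peanut step. So the step is missing in the one case where it could be useful, an active day 2.

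**6. Which results could be touched.** Challenge is the preferred way to determine peanut allergy for the participant co-primary endpoint (Protocol 3.3.1; SAP 8.2.1.1). The sibling co-primary endpoint is sensitization by IgE or skin prick and uses no challenge. LEAP participants must be at least 9.5 years old, so the text for 36 months or younger can apply only to siblings. Their peanut allergy is a secondary endpoint (SAP 8.3.9: "Peanut allergy status in the LEAP Siblings and LEAP Parents at V144 will be determined using the same criteria" as in LEAP participants).

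**The case against.** The strongest reply is that the intent is clear and the consequence slight. Most of it stands.

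- **Intent.** A reader might infer that the plan puts peanut into the placebo day and that the physician cannot prevent it. The documents do not support that. The procedure is placebo-controlled, and the dietician holds the code and can prepare a low-step meal as placebo. In the day 2 text, the rule that one day is peanut and the other placebo comes immediately before the low-dose sentence. The steps are also optional, so the physician can leave them out. What remains is that the sentences should state what they mean.
- **The missing step.** A reader might infer that an active day 2 cannot start at 0.01 g. The text does not offer that step on day 2, but nothing forbids it, and 0.03 g is still available.
- **Interpretability.** A reader might infer that the challenge can be interpreted only if the placebo day is wholly free of peanut. The protocol does not require that. If the day 2 blinded doses pass without reaction, it adds an open peanut dose that day (5 g or 2.0 g by age group), including when day 2 is the placebo day. The point concerns the blinded part only.
- **Who reaches a DBPCFC.** After an inconclusive open challenge the child has already eaten peanut, and an at-risk child had 0.01 g available there. The other route is investigator discretion, with food aversion and anxiety as the examples. Nothing in the documents shows a child harmed by starting at 0.03 g. The second route, however, does not guarantee an earlier graded exposure.

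None of this explains why day 1 offers 0.01 g and day 2 does not.

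**Conclusion.** The point holds as a minor dosing and wording fault in both age groups. A child whose active day is day 2 is offered 0.03 g as the lowest first step instead of 0.01 g, three times higher and 0.02 g more, with no reason given. This result assumes that the low steps follow the day's code, which the blinding rule implies but the low-dose sentences do not state. On the literal text, the blinded part of a placebo day would include 0.03 to 0.04 g of peanut when the steps are used.

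Only two-day DBPCFCs that use the optional steps are affected. The documents do not give their number; it is probably small. It would be tempting to infer misclassified allergy in the participant co-primary endpoint, because challenge is its preferred determination, but nothing in the documents shows an effect on that result. The sibling co-primary endpoint does not use a challenge at all.

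**What to change.** In Protocol 6.7.1.2.1, for both age groups, offer the same optional 0.01 g and 0.03 g steps on day 1 and day 2, and state that they are given as peanut protein or matched placebo according to that day's code.

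The active day could then start at 0.01 g whichever day it fell on. The placebo day would have 0 g of peanut in its blinded part. With both steps used, blinded peanut would be 4.35 + 0.04 = 4.39 g (over 36 months) or 1.85 + 0.04 = 1.89 g (36 months or younger) in either order. The rule for the final open dose needs no change.

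The cost is a wording change and one further optional meal (0.01 g peanut or matched placebo) for the dietician to prepare on day 2.
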